Less likely adverse effects (< 20%) are leukopenia, neutropenia, abdominal pain, and mucositis/stomatitis. Also reported on vorinostat trials, but with the relationship to vorinostat still undetermined: allergy/immunology (vasculitis), cardiovascular (palpitations, tachycardia, hypertension, hypotension), coagulation (INR, PTT alterations), constitutional symptoms (fever, insomnia, rigors/chills, weight loss), death, dermatology/skin (alopecia, ecchymosis, pruritus, rash), gastrointestinal (colonic obstruction, dysphagia, esophagitis, flatulence, gastritis, heartburn, hemorrhage/bleeding (epistaxis. hemoptysis. melena. petechiae. subdural hematoma), infection (febrile neutropenia, infection), lymphatics (limb edema, swelling face), metabolic/laboratory (alkaline phosphatase, hyperbilirubinemia, hypercalcemia, hyperkalemia, hypermagnesemia, hypernatremia, hyperuricemia, hypoalbuminemia, hypomagnesemia, hyponatremia, low serum bicarbonate), musculoskeletal/soft tissue (gait/walking, rib fracture), neurology (ataxia, confusion, sensory neuropathy, speech impairment, depression. dizziness. tremor). ocular/visual (eyelid ptosis), pain (back pain, chest pain, face pain, flank pain, gingival pain, groin pain, headache, joint pain, limb pain, muscle pain, neck pain, pharyngolaryngeal pain), pulmonary/upper respiratory (dyspnea, hiccoughs, pleural sinus congestion. pneumonitis/pulmonary infiltrates, effusion. wheezina). renal/genitourinary (urinary frequency, urinary incontinence, urinary retention), vascular (deep vein thrombosis).

Dose limiting toxicities are anorexia, dehydration, diarrhea, and fatigue. Prothrombin time and INR prolongations have been reported in patients taking vorinostat concomitantly with coumarin derivative anticoagulants. Thus, monitor these patients more frequently for alterations in their coagulation parameters may be necessary.

To prevent dehydration, patients should consume at least 2 liters of fluid orally, daily. If patients are experiencing dysgeusia, popsicles or Gatorade may be recommended. If diarrhea occurs, it should be managed with loperamide according to institutional guidelines. Nausea should be managed according to standard practice; 5HT-3 antagonists have proven effective.

Vorinostat was evaluated in a panel of genetic toxicity assays; *in vivo* and *in vitro* assays were found to be positive. Therefore, vorinostat should not be taken by pregnant women. Both women and men of reproductive potential participating in vorinostat studies must be completely informed of the unknown risks of pregnancy and agree not to become pregnant or father a child during the time they are participating in the study until at least 30 days after the final dose. Further, appropriate contraception must be used.

Vorinostat-related Clinical or Laboratory Adverse Experiences by Preferred Term as experienced by \ge 10% of all Patients

	Total Patients (N=305)		
	Related Experiences Only		
	All Grades	Grade 3-5	
	n %	n %	
Fatigue	195 (63.9)	42 (13.8)	
Nausea	170 (55.7)	17 (5.6)	
Diarrhoea	151 (49.5)	14 (4.6)	
Anorexia	141 (46.2)	15 (4.9)	
Vomiting	100 (32.8)	5 (1.6)	
Hyperglycaemia	79 (25.9)	10 (3.3)	
Blood Creatinine Increased	75 (24.6)	2 (0.7)	
Weight Decreased	75 (24.6)	4 (1.3)	
Thrombocytopenia	69 (22.6)	34 (11.1)	
Constipation	54 (17.7)	3 (1.0)	
Dysgeusia	54 (17.7)	0 (0.0)	
Haemoglobin Decreased	53 (17.4)	10 (3.3)	
Dehydration	45 (14.8)	25 (8.2)	
Hypocalcaemia	42 (13.8)	3 (1.0)	
Platelet Count Decreased	41 (13.4)	13 (4.3)	
Dyspnoea	40 (13.1)	1 (0.3)	
Anaemia	36 (11.8)	7 (2.3)	
Hyponatraemia	36 (11.8)	5 (1.6)	
Alopecia	35 (11.5)	0 (0.0)	
Dry Mouth	35 (11.5)	0 (0.0)	
Aspartate Aminotransferase Increased	34 (11.1)	2 (0.7)	
Alanine Aminotransferase Increased	33 (10.8)	1 (0.3)	
Hypokalaemia	33 (10.8)	6 (2.0)	
Blood Alkaline Phosphatase Increased	31 (10.2)	1 (0.3)	
Hypoalbuminaemia	31 (10.2)	1 (0.3)	
White Blood Cell Count Decreased	31 (10.2)	4 (1.3)	
A patient is counted only once within a specific preferred term, even if more than one adverse experience with specific preferred term occurred. Adverse experience terms are from MedDRA Version 8.1			

3.3 Temozolomide

3.3.1 Therapeutic Classification

Alkylator agent, antineoplastic.

3.3.2 Pharmacologic Data

Temozolomide (TMZ, Temodar®) is an orally administered alkylating agent with activity against malignant gliomas. It is a prodrug that spontaneously converts at physiologic pH to the active alkylating agent 5-(3- methyltriazen-1-yl)imidazole-4-carboximide (MTIC) under physiologic conditions. The cytotoxicity of temozolomide is principally mediated through methylation of DNA at the O6 position of guanine Temozolomide is rapidly and completely absorbed after oral administration; peak plasma concentrations occur in 1 hour. Food reduces the rate and extent of

temozolomide absorption. Mean peak plasma concentration and AUC decreased by 32% and 9%, respectively, and Tmax increased 2-fold (from 1.1 to 2.25 hours) when temozolomide was administered after a modified high-fat breakfast.

Temozolomide is rapidly eliminated with a mean elimination half-life of 1.8 hrs and exhibits linear kinetics over the therapeutic dose range. Temozolomide has a mean apparent volume of distribution of 0.4 L/kg (%CV=13%). It is weakly bound to plasma proteins; the mean percent bound of drug-related total radioactivity is 15%.

Temozolomide is spontaneously hydrolyzed at physiologic pH to the active species MTIC and to temozolomide acid metabolite. MTIC is further hydrolyzed to 5-aminoimidazole-4-carboxamide (AIC), which is known to be an intermediate in purine and nucleic acid biosynthesis and to methylhydrazine, which is believed to be the active alkylating species. Cytochrome P450 enzymes play only a minor role in the metabolism of temozolomide and MTIC. Relative to the AUC of temozolomide, the exposure to MTIC and AIC is 2.4% and 23%, respectively. Approximately 38% of the. administered temozolomide total radioactive dose is recovered over 7 days: 37% in urine and 0.8% in feces. The majority of the recovery of radioactivity in urine is as unchanged temozolomide (5.6%) AIC (12%), temozolomide acid metabolite (2.3%), and unidentified polar metabolite(s) (17%). Overall clearance of temozolomide is ~5.5 L/hr/m.

3.3.3 Pharmaceutical Data

Temozolomide is not directly active but undergoes rapid non-enzymatic conversion at physiologic pH to the reactive compound MTIC. The cytotoxicity of MTIC is thought to be primarily due to alkylation of DNA. Alkylation (methylation) occurs mainly at the O6 and N7 positions at guanine. Temozolomide should be stored at room temperature. The capsules are packaged in 30 cc 28 mm-48-Type I amber glass bottles (30 capsules/bottle) and should be stored between 2 and 30 degrees Centigrade. Capsules are stable for at least 30 months when stored in amber glass bottles at this temperature.

3.3.4 Usual Dosage Range

The typical dose regimen for patients with recurrent malignant glioma is 150 -200 mg/m2/day orally days 1-5 every 28 days [12]. According to clinical circumstances the initial dosage may require reduction by 20 to 25% in patients with risk factors such as prior myelosuppressive therapy and poor performance status. Determining haematologic nadir by frequent blood counts during initial courses is recommended for future dosage adjustment and scheduling of temozolomide.

3.3.5 Route of Administration

Oral.

3.3.6 Formulation

Temozolomide (Temodar®) is supplied in white, opaque, preservative free, 2-piece, hard gelatin capsules in the following p.o. dosage strengths: 5 mg, 20 mg, 100 mg, 140 mg, 180 mg and 250 mg. Capsules should not be opened or chewed. If capsules are accidentally opened or damaged, inhalation or contact with the skin should be avoided. Each capsule contains drug substance in combination with lactose, anhydrous NF, colloidal silicon dioxide NF, sodium starch glycolate NF, tartaric acid NF, and stearic acid NF. The capsule shells contain gelatin NF, titanium dioxide USP, and sodium lautyl sulfate NF.

3.3.7 Supply: Provided by Merck, Sharp and Dohme.

3.3.8 Side Effects and Toxicities

3.3.8.1 Known Potential Adverse Events

Hematologic: Thrombocytopenia, leukopenia, myelodysplastic syndrome Gastrointestinal: Nausea, vomiting, anorexia Hepatic: Elevated liver enzymes (reversible) Skin: Rash

Neurologic: Convulsions, weakness (one side of the body), incoordination, paralysis Other: Constipation, diarrhea, stomatitis, fatigue, decreased performance status, headache

A. Likely (occurring in more than 20% of patients)

• fatigue

alopecia

constipation

- headacheseizures
- nauseavomiting

- anorexia
- Lymphopenia
- B. Common (occurring in 3-20% of patients)

2006-0709 March 4, 2011 Page 23 of 57

- dizziness
- abnormal muscle movements/ coordination
- abnormal gait
- hemiplegia or partial paralysis
- upper and/or lower extremity edema
- weakness (such as weakness on one side of the body)
- tickling/tingling sensation
- pain (such as in the abdomen, joints, back, and/or muscles)
- breast pain in females
- memory problems

- depression
- difficulty sleeping
- drowsiness
- skin rash
- pruritus
- dry skin
- mucositis
- dysphagia
- dysgeusia taste or changes
- diarrhea
- excess steroid in the (possible body bruising and/or increase in size of the face and/or neck)
- viral infection
- anxiety
- leukopenia

- weight gain
- loss of urinary control
- urinary tract infection
- frequent urination
- abnormal vision
- blurry vision
- diplopia or double vision
- fever
- cough
- sore throat
- sinusitis
- dyspnea
- allergic reaction
- confusion
- neutropenia thrombocytopenia

C. Rare but serious (occurring in fewer than 3% of patients)

- disease bone marrow where not enough blood cells are made
- hallucinations
- nervous system disease
 severe skin damage (possible pain and/or weakness)
- neuropathies (nerve damagepossible numbness, tingling, and pain)
- hyperglycemia (possible diabetes)
- hypokalemia (possible weakness)
- severe allergic reaction

- of • new occurrence (including cancer myeloid leukemia)
- allergic skin reaction
- with loss of a large portion of skin
- weight loss
- fever due to low white blood cell counts
- bruising
- hemorrhage
- Steven-Johnson Syndrome

- damage from radiation (such as skin damage)
- pneumonitis (lung inflammation)
- flu-like symptoms
- injection site reactions (skin redness. irritation, pain, itching, swelling, and/or warmth)
- opportunistic infection
- herpes infection causing painful skin rash (shingles)

3.3.9 **Special Populations:**

Creatinine Clearance: Population pharmacokinetic analysis indicates that 3.3.9.1 creatinine clearance over the range of 36-130 mL/min/m² has no effect on the

clearance of temozolomide after oral administration. The pharmacokinetics of temozolomide have not been studied in patients with severely impaired renal function (CLcr < 36 mL/min/m²). Caution should be exercised when temozolomide is administered to patients with severe renal impairment. Temozolomide has not been studied in patients on dialysis.

Hepatically Impaired Patients: 3.3.9.2 In a pharmacokinetic study, the pharmacokinetics of temozolomide in patients with mild to moderate hepatic impairment (Child's-Pugh Class I-II) were similar to those observed in patients with normal hepatic function. Caution should be exercised when temozolomide is administered to patients with severe hepatic impairment.

3.3.9.3 Gender: Population pharmacokinetic analysis indicates that women have an approximately 5% lower clearance (adjusted for body surface area) for temozolomide than men. Women have higher incidences of grade 4 neutropenia and thrombocytopenia in the first cycle of therapy than men.

3.3.9.4 Age: Population pharmacokinetic analysis indicates that age (range 19-78) years) has no influence on the pharmacokinetics of temozolomide. In the anaplastic astrocytoma study population, patients 70 years of age or older had a higher incidence of grade 4 neutropenia and grade 4 thrombocytopenia in the first cycle of therapy than patients <70 years of age. In the entire safety database, however, there did not appear to be a higher incidence in patients \geq 70 years of age.

3.3.9.5 Drug-Drug Interactions: In a multiple dose study, administration of temozolomide with ranitidine did not change the Cmax or AUC values for temozolomide or MTIC. Population analysis failed to demonstrate any influence of co-administered dexamethasone, prochlorperazine, phenytoin, carbamazepine, ondansetron, H₂-receptor antagonists, or phenobarbital on the clearance of orally administered temozolomide.

The following side effects have been reported in research studies with temozolomide. However, their causality related to temozolomide is uncertain:

- BUN blood level increase
 - death
- creatinine blood elevated hypoxia
- lymphopenia
- weight loss • epistaxis
- thrombocytopenia neutropenia
- sepsis

- cholecystitis
- pancreatitis
- GI perforation
- dehydration

3.3.9.6 Temozolomide is potentially mutagenic and should be handled with appropriate precautions by both staff and patients. Capsules should not be opened. If capsules are accidentally opened or damaged, rigorous precautions should be taken with the capsule contents to avoid inhalation or contact with the skin or mucous membranes. Procedures for proper handling and disposal of anticancer drugs should be considered.

3.3.10 Contraindications: Temozolomide is contraindicated in patients who have a history of a hypersensitivity reaction to any of its components or to DTIC.

3.3.11 Pregnancy Category D

Temozolomide may cause fetal harm when administered to a pregnant woman. There are no adequate and well-controlled studies in pregnant women. If this drug is used during pregnancy, or if the patient becomes pregnant while taking this drug, the patient should be apprised of the potential hazard to the fetus. **Women of childbearing potential should be advised to avoid becoming pregnant during therapy with temozolomide.**

Treatment of a man with temozolomide may increase the risk of birth defects if he causes a woman to become pregnant while he is taking temozolomide. Men treated with temozolomide may have difficulty causing a woman to become pregnant after their treatment is completed. Men receiving temozolomide should be directed to use effective contraception while they are being treated. There is insufficient data to know what the risk of subsequent problems with fertility will be. Similarly, women who are treated with temozolomide may have difficulty becoming pregnant in the future and may at be at increased risk of having children with birth defects. There is insufficient evidence to determine what the risk of these complications will be.

4.0 ELIGIBILITY CRITERIA

- **4.1** Patients with histologically proven supratentorial glioblastoma multiforme, gliosarcoma or anaplastic glioma will be eligible for the Phase I component of this protocol. Anaplastic gliomas include anaplastic astrocytoma (AA), anaplastic oligodendroglioma (AO), anaplastic mixed oligoastrocytoma (AMO), or malignant glioma NOS (not otherwise specified). Patients will be eligible if the original histology was low-grade glioma and a subsequent histological diagnosis of a malignant glioma is made. Only patients with histologically proven supratentorial glioblastoma multiforme or gliosarcoma will be eligible for the Phase II component.
- **4.2** Patients must have shown unequivocal evidence for tumor recurrence or progression by MRI scan and should have failed radiation therapy. The scan done prior to study entry documenting progression will be reviewed by the treating physician to document changes in tumor dimension to confirm recurrence. Patients with prior therapy that included interstitial brachytherapy or stereotactic radiosurgery must have confirmation of true progressive disease rather than radiation necrosis.
- **4.3** Patients may have had up to 2 prior relapses provided the functional status and other eligibility criteria for enrollment are met.
- **4.4** All patients must sign an informed consent indicating their awareness of the investigational nature of this study in keeping with the policies of this hospital.

- **4.5** The baseline on-study MRI should be performed within 14 days (+ 3 working days) prior to registration and on a steroid dosage that has been stable or decreasing for at least 5 days. If the steroid dose is increased between the date of imaging and the initiation of therapy (or at that time), a new baseline MRI is required. The same type of scan, i.e., MRI, must be used throughout the period of protocol treatment for tumor measurement.
- **4.6** Patients having undergone recent resection of recurrent or progressive tumor will be eligible as long as all of the following conditions apply:

a) They have recovered from the effects of surgery.

b) Evaluable or measurable disease following resection of recurrent tumor is not mandated for eligibility into the study.

c) To best assess the extent of residual measurable disease post-operatively, a MRI should be done no later than 96 hours in the immediate post-operative period or 4-6 weeks post-operatively.

- **4.7** Patients must be 18 years old or older.
- **4.8** Patients must have a Karnofsky performance status (KPS) equal or greater than 60 (Appendix G).
- **4.9** Patients must have recovered from the toxic effects of prior therapy to < grade 2 non hematological or grade 2 or lesser hematological toxicity per CTC ver 3 (except deep vein thrombosis see section 5.3): 4 weeks from prior cytotoxic therapy and/or at least two weeks from vincristine, 6 weeks from nitrosoureas, 3 weeks from procarbazine administration, and 1 week for non-cytotoxic agents, e.g., interferon, tamoxifen, cis-retinoic acid, etc. (radiosensitizer does not count). Patients who receive anticancer agents for non-therapeutic purposes unrelated to this study (such as presurgically for obtaining pharmacology data for the agent) will be eligible to enter the study provided they have recovered from the toxic effects of the agent if any. Because the trial is based on the hypothesis that the combination of agents used will be synergistic in their effects, and that HDAC inhibition will potentially overcome resistance to retinoids, prior treatment with cRA is allowed. Any questions related to the definition of non-cytotoxic agents should be directed to the Study Chair.
- **4.10** Patients must have adequate bone marrow function (ANC \geq 1,500/mm³ and platelet count of \geq 100,000/mm³), adequate liver function (SGPT \leq 3 times normal and alkaline phosphatase \leq 2 times normal, bilirubin \leq 1.5 mg/dl), adequate renal function (BUN and creatinine \leq 1.5 times institutional normal) and normal serum amylase and lipase prior to starting therapy. Elevated cholesterol and triglycerides are not a contraindication to study enrollment, but should be managed as clinically appropriate by the treating physician.
- **4.11** Patients with a history of any other cancer (except non-melanoma skin cancer or carcinoma in-situ of the cervix or bladder), unless in complete remission and off of all therapy for that disease for a minimum of 3 years are ineligible.

- **4.12** Patients must not have:
 - a) active infection

b) disease that will obscure toxicity or dangerously alter drug metabolism, especially liver disease including cirrhosis or hepatic dysfunction

c) serious intercurrent medical illness

d) prior recurrence with other HDAC inhibitors. However, patients who have received anticancer agents for non-therapeutic purposes (for eg., as part of a pharmacology study without therapeutic intent) will remain eligible for enrollment into the study

- **4.13** Patients receiving valproic acid (VPA), an anticonvulsant drug with HDAC inhibitor properties, will be excluded, unless they are switched to an alternative agent prior to treatment initiation. No wash out period is required.
- **4.14** Prior treatment with dose dense regimens of temozolomide is not allowed (e.g, 7 days on/7 days off, 21 day/28 day and daily low dose continuous dosing). However, standard day 1-5 dosing and low dose daily dosing as part of chemoradiation therapy are allowed.
- **4.15** Patients receiving treatment with other antiepileptic medications will not be excluded. Vorinostat is not metabolized by cytochrome P450 3A4 (CYP 3A4). However, vorinostat may potentially suppress CYP 3A4 activity. Therefore, patients should preferably be treated with non-enzyme inducing anti-epileptic medications to avoid any potential interactions with vorinostat. However, the use of non-enzyme inducing anti-epileptic medications is not mandatory. If enzyme-inducing antiepileptic drugs are used, monitoring of drug levels should be considered, as considered clinically appropriate by the treating physician.
- **4.16** Patients with a known allergy to any component of vorinostat, or a known allergy to temozolomide and/or isotretinoin will be excluded.
- **4.17** Patients must be willing and able to comply with the FDA mandated iPLEDGE program for treatment with isotretinoin (cRA). Patients must sign specific informed consents for treatment with cRA, as mandated by iPLEDGE guidelines. Women of childbearing potential must not be pregnant, must not be breast-feeding and must practice adequate contraception (please refer to 6.4 and Appendix I for details and definitions woman of childbearing potential; adequate methods of contraception).
- **4.18** Male patients on treatment with vorinostat must agree to use an adequate method of contraception for the duration of the study, and for 30 days after the last dose of study medication (please refer to Appendix I for definition of adequate methods of contraception).
- **4.19** Patient must be able to tolerate the procedures required in this study including periodic blood sampling, study related assessments, and management at the

treating institution for the duration of the study. Inability to comply with protocol or study procedures (for example, an inability to swallow tablets) will be an exclusion criteria.

- **4.20** This study was designed to include women and minorities, but was not designed to measure differences of intervention effects. Males and females will be recruited with no preference to gender.
- **4.21** No exclusion to this study will be based on race. The malignant glioma patient population treated at MDACC over the past year is as follows:

American Indian or Alaskan Native - 0 Asian or Pacific Islander - <2% Black, not of Hispanic Origin - 3% Hispanic - 6% White, not of Hispanic Origin - 88% Other or Unknown - 2% Total-100%

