General disorders and Administration	Fatigue, pyrexia, chills, edema peripheral	
Site Conditions		
Investigations	Blood creatinine increased, weight decreased,	
C C	hemoglobin decreased, aspartate	
	aminotransferase increased, platelet count	
	increased, prothrombin time prolonged,	
	alanine aminotransferase increase	
Metabolism and Nutritional Disorders	Anorexia, hyperglycemia	
Musculoskeletal, and Connective	Muscle spasm	
Tissue Disorders		
Nervous System Disorders	Dizziness, dysgeusia	
Respiratory, Thoracic and	Cough, dyspnea	
Mediastinal Disorders		
Skin and Subcutaneous Tissue	Alopecia	
Disorders		

Certain classes of patients were excluded from the clinical studies conducted to date, i.e., patients with significant hepatic or renal impairment or other major medical conditions that could have interfered with evaluation of study drug. In addition, patients who were pregnant or nursing were excluded from these studies. No formal studies evaluating the effect of age, gender, race or organ function (such as liver, kidney) on the pharmacokinetics and pharmacodynamics of vorinostat have been conducted. Accordingly, there are no clinical data for these populations.

Prolongation of prothrombin time (PT) and International Normalized Ratio (INR) were observed infrequently in patients receiving vorinostat concomitantly with coumarin-derivative anticoagulants. Physicians should carefully monitor PT and INR in patients concurrently administered vorinostat and coumarin derivatives.

Vorinostat should not be administered concomitantly with other HDAC inhibitors (e.g., valproic acid) as class-specific adverse reactions may be additive. Severe (Grade 4) thrombocytopenia with associated gastrointestinal bleeding and anemia has been reported with the concomitant use of vorinostat and valproic acid.

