5.0 TREATMENT PLAN

5.1. Phase I Component

The Phase I component of the trial was designed with three treatment arms (see below). This component is a non randomized trial in which Arm 1 and Arm 2 were to be opened simultaneously with consecutive patients enrolled alternately to each arm, and sequentially to each dose level. If the MTD was reached earlier in one arm, all subsequent patients were to be enrolled to the other arm. Once the MTD for Arm 1 and Arm 2 was known, Arm 3 would begin accrual. A maximum of 54 patients were to be enrolled in this component of the trial. The MTDs obtained in the Phase I component were planned to be used as the Phase II dose in the next component of the trial.

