5.1.3. Arm 3 – Vorinostat plus isotretinoin plus temozolomide

This arm will assess the MTD of vorinostat and temozolomide in combination with fixed doses of cRA. The enrollment will proceed as outlined for Arm 1 and 2 (cohorts of 3 patients enrolled to each dose level), declaring MTD for vorinostat in combination with temozolomide and cRA once DLT is noted. In this arm, cRA will be given on days 1-21 and vorinostat on days 1-7 and 15-21. Temozolomide will be administered orally on days 1-7 and 15-21. Days 22-28 will be considered a notreatment "rest" period. A maximum of three dose levels of vorinostat will be used as shown in the table below.

Level	Arm 3		
	Vorinostat	cRA	Temozolomide
	(mg/day x days 1-7 &	(mg/m2/day x 21	(mg/m2/day on
	15-21)	days)	days 1-7 & 15-21

-111	300	100	100
-11	300	100	125
-1	400	100	125
0 (starting dose)	400	100	150
I	500	100	150

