5.2.2. Surgical Arm

Ten patients who require resection for recurrent glioblastoma multiforme will be included in this arm of the study. These patients will receive treatment with vorinostat at a dose of 400 mg once daily for 3 consecutive days prior to surgery. Blood samples for acetylation status of histones and p21 levels in peripheral mononuclear cells will be collected at baseline prior to treatment, and after the first dose of vorinostat. The last dose prior to surgery will be administered the morning of surgery within 6 hours of the tumor removal. Tumor tissue and intraoperative blood samples will be obtained for analysis of drug levels, histone acetylation and p21 levels. Approximately 2 weeks after surgery is performed, each patient will be randomized to one of the three treatment arms of the phase II component (arm 1: vorinostat + cRA; arm 2: TMZ + cRA; arm 3: vorinostat + cRA + TMZ). Patients enrolled in arms 1 and 3 will be evaluated with blood samples before and after treatment with vorinostat in cycles 1 and 2 as described for patients in the non-surgical arm (see 5.2.1, and 7.10). In surgical patients, cycle 1 will be the first cycle of treatment after surgery.

Progression Free Survival (PFS) in patients enrolled in the surgical arm will be determined from the date of randomization into the chemotherapy arms (i.e. after surgery for resection of recurrent tumor), and not from the date of registration in the trial.

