6.0 PRE-STUDY EVALUATION

- **6.1** A complete history and neurological examination (including height, weight and Karnofsky Performance Status), as well as documentation of evaluable disease shall be performed on all patients within 14 days (+ 3 working days) of study entry.
- **6.2** The treating physician will review a Gd-DPTA MRI scan done prior to study entry documenting progression. For non-surgical arm patients, a baseline scan should be performed within 14 days (+ 3 working days) of registration, with day 0=registration date. The baseline on-study MRI should be performed on a steroid dosage that has been stable or decreasing for at least 5 days. If the steroid dose

is increased between the date of imaging and the initiation of therapy (or at that time), a new baseline MRI is required.

- **6.3** Pre-treatment laboratory tests will include CBC, differential, platelets, PT, PTT, INR, total protein, albumin, calcium, phosphorus, magnesium, glucose, BUN, creatinine, sodium, potassium, uric acid, total bilirubin, alkaline phosphatase, LDH, SGPT (ALT), SGOT (AST), amylase, lipase, lipid panel (total cholesterol, HDL-cholesterol, LDL-cholesterol, triglycerides), and a pregnancy test for women of child bearing potential (see 6.4 and Appendices I and J). Anticonvulsant levels in patients on treatment with enzyme-inducing antiepileptic drugs (phenytoin, phenobarbital, carbamazepine) will also be obtained if considered appropriate by the treating physician. Blood tests must be performed within 14 days (+ 3 working days) of registration, with day 0 = registration date. Pregnancy test must be obtained 24 hours before treatment with isotretinoin starts. Patients whose clinical condition has significantly changed between the time of these tests and the initiation of treatment in the judgement of the treating physician, will have a repeat chemistry panel prior to the start of treatment.

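### Minor eligibility correction: 4.16 does not exclude a past DTIC hypersensitivity reaction, for which 3.3.10 contraindicates temozolomide

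*Combined protocol and SAP*

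**What the plan says.** Section 3.3.10, in the temozolomide drug background, states: "Temozolomide is contraindicated in patients who have a history of a hypersensitivity reaction to any of its components or to DTIC". Section 4.16, the only eligibility criterion on allergy, states: "Patients with a known allergy to any component of vorinostat, or a known allergy to temozolomide and/or isotretinoin will be excluded".

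Temozolomide is given in the Phase I arm still to be studied, Arm 3 (5.1.3: "Temozolomide will be administered orally on days 1-7 and 15-21"). It is also given in two of the three Phase II arms: Arm 2 with isotretinoin, and Arm 3 with vorinostat and isotretinoin. Under 11.2, the first 30 Phase II patients are allocated equally and later allocation follows the accruing data. In the surgical arm (5.2.2), patients take vorinostat for 3 days before resection. About 2 weeks after surgery, "each patient will be randomized to one of the three treatment arms of the phase II component".

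Section 6.1 requires a full history within 14 days (plus 3 working days) of study entry. The efficacy analysis in 11.2 is by intent to treat among patients who are both randomized and eligible.

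**The concern.** Screening staff work from the eligibility list. When the protocol itself states an absolute contraindication to a study drug, that list is where it should take effect, especially when the drug is then assigned by randomization. Here the list carries over part of the contraindication (allergy to temozolomide) and leaves out the part that concerns DTIC.

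At stake is a patient who passes the listed criteria and is then assigned a drug that the same protocol says must not be given. Either someone notices, and the patient cannot be treated as assigned, or nobody notices, and the patient is exposed. If the patient met the criteria as written, the patient also stays in the intent-to-treat set. For a surgical patient, a conflict seen only at allocation comes after study vorinostat and an operation.

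**Working it through.** No formula applies, and the plan has no figure on this point to reproduce. The check compares the texts.

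**1. The two statements side by side**

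| Hypersensitivity to | 3.3.10 contraindicates temozolomide | 4.16 excludes |
|---|---|---|
| Temozolomide | Yes | Yes |
| Any component of temozolomide | Yes | Not stated; the phrase is attached only to vorinostat |
| DTIC | Yes | No |

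The second row is a difference of wording, since an allergy to temozolomide can be read to include the capsule ingredients. The third row is a gap, because 3.3.10 lists DTIC separately from temozolomide's own components.

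**2. Could another criterion close the gap?**

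- 4.9 sets recovery and washout after prior therapy. It names several agents, but not DTIC.
- 4.11 concerns other cancers. It admits patients in complete remission and off therapy for at least 3 years.
- 4.12 covers infection, disease that obscures toxicity or alters drug metabolism, serious intercurrent illness, and prior recurrence with HDAC inhibitors. A past drug reaction is none of these.
- 4.14 concerns prior dose-dense temozolomide.
- 4.19 concerns tolerating and complying with study procedures. It is taken up under the objection.
- The remaining criteria in 4.1 to 4.21 do not touch drug hypersensitivity.
- In 6.1 to 6.7, only the history in 6.1 could bring a DTIC reaction to light. No criterion then says that it excludes the patient.

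The criteria are numbered without a break from 4.1 to 4.21. The appendices and consent pages were not available, so the claim is limited to sections 4 and 6.

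**3. Can an eligible patient be assigned temozolomide?**

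- Phase I Arm 3: yes, every patient receives it.
- Phase II, first 30 patients: equal allocation puts the chance of a temozolomide arm at 1/3 + 1/3 = 2/3.
- Phase II thereafter: the chance moves with the data.

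**4. How many patients?**

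The documents report neither the frequency of prior DTIC use nor the frequency of reactions to it, so there is no input for an estimate. For scale only, any one such patient would be 1/135 = 0.7% of the maximum Phase II sample. This is not a prediction that there will be one.

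**The case against.** The strongest case on the other side is that the protocol already forbids the harmful act. Section 3.3.10 is current text of the same document, so dosing such a patient would go against the protocol. The history in 6.1 may reveal the reaction. Phase I leaves time to notice (5.1: "This component is a non randomized trial"), and under 11.2 the Phase II allocation is shown to the user on screen. All of this stands, and it is why exposure is the less likely outcome.

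The population narrows the gap further. Section 2.1 describes wide first-line use of temozolomide, 4.2 requires failed radiation, and 4.14 allows prior standard temozolomide. Many candidates will have had the drug, and 4.16 removes those known to be allergic to it. In the text reviewed, DTIC appears only in 3.3.10. This also stands.

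It can also be argued that 4.19 excludes the patient, because someone barred from temozolomide cannot comply with a randomization in which two of three arms contain it. That reading is strained. The criterion is about procedures and compliance, with swallowing tablets as its example, and a screener would not take from it a question about DTIC.

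A comparison with valproic acid is tempting. The warning in 2.3.4.1 ("Vorinostat should not be administered concomitantly with other HDAC inhibitors (e.g., valproic acid) as class-specific adverse reactions may be additive") did become an entry rule in 4.13 ("Patients receiving valproic acid (VPA), an anticonvulsant drug with HDAC inhibitor properties, will be excluded"). That shows the protocol can turn a drug-background warning into a criterion. It does not show an inconsistent policy: valproic acid is a concurrent anticonvulsant in a population that often needs one, and 2.3.4.1 reports severe events with the combination. A past reaction to a non-study drug is a different matter.

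**Conclusion.** The mismatch is real and the correction is worth making, at the lowest priority. As written, the entry rule admits a patient whom 3.3.10 says must not receive temozolomide. The likely consequence is a randomized patient who cannot be treated as assigned.

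A reader might infer more, and the documents do not support it:

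- That the protocol allows contraindicated dosing. It does not, since 3.3.10 prohibits it.
- That a given number of patients is at risk. No count can be derived. Close to zero is a judgement from the population described in sections 2 and 4, not a calculation.
- That the comparison of the arms is threatened. An isolated patient kept in the intent-to-treat set without the assigned treatment would not materially change a trial of up to 135 patients, and no sample size, stopping rule or operating characteristic depends on this point.

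The conclusion rests on sections 4 and 6 as supplied, and on reading 4.19 in its ordinary sense.

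**What to change.** Reword 4.16 along these lines: *Patients with known allergy or hypersensitivity to any component of vorinostat, temozolomide or isotretinoin, or to DTIC, are excluded.* The necessary addition is DTIC. Extending the component wording to temozolomide aligns the criterion with 3.3.10, and extending it to isotretinoin keeps the sentence uniform.

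Add the question to the 6.1 history, to be answered before registration. For surgical patients it must be answered before the first presurgical dose of vorinostat.

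The cost is a few words and one screening question. Accrual should be practically unaffected, and nothing in section 11 needs to change.
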